2.5.3 Safety Variables

AEs are only recorded if they occur in a temporal relationship with drawing of the two blood samples on visits 1 and 2 as these are the only measures carried out in addition to the routine procedures at the site and, hence, for the sole purpose of the study (interventions). A causal relationship of any adverse events with hhCG testing is impossible as a patient's test results will not be made known during the course of the study. Hence, the patients' course during and after the study cannot be influenced by any inaccurate test values or the interpretation of the hhCG values (accurate or inaccurate).

Incidents will be documented following the guidance provided in MEDDEV 2.12.-1 rev. 6 and local regulations and guidelines. Indirect harms are not possible to occur as discussed in section 4.3.2.

2.6 Known and Potential Risks and Benefits

Apart from two additional blood drawings on visits 1 and 2 there will be no further measures (interventions) during the study in addition to such procedures as are part of the clinical

routine at the site. Except for the known and generally accepted risks involved with drawing blood samples, no further risks nor any benefits for the patients are involved.

3 MATERIALS

The project is supported by Roche Diagnostics Centralised and Point of Care Solutions within the scope of a research agreement between IVI Valencia and Roche Diagnostics Centralised and Point of Care Solutions.

4 EVALUATION REQUIREMENTS

4.1 Data Management Plan

Clinical, laboratory and test result data will be entered into an eCRF. A limited range of validation checks will be detailed in a manual and implemented into the eCRF as appropriate. For data analysis SAS software will be used. The study database shall be made available to Roche Diagnostics and the study site in an agreed upon format and data transfer mode.

4.2 Safety of Specimen Handling

For specimen handling the local safety regulation will apply to rule out any possible biological hazard.

4.3 Safety Assessment

4.3.1 Adverse Events

AEs are only recorded if they occur in a temporal relationship with the blood drawings on visits 1 and 2 as these are the only measures carried out in addition to the routine procedures at the site and, hence, for the sole purpose of the study (interventions). A causal relationship of any adverse events with hhCG testing is impossible as a patient's test results will not be made known during the course of the study. Hence, the patients' course during and after the study cannot be influenced by any inaccurate test values or the interpretation of the hhCG values (accurate or inaccurate).

4.3.2 Incidents and Indirect Harms

The documentation and reporting of incidents will follow the guidance provided in MEDDEV 2.12.-1 rev. 6 and local regulations and guidelines.

An incident is any malfunction or deterioration in the characteristics and/or performance of a device, as well as any inadequacy in the labelling or the instructions for use which, directly or indirectly, might lead to or might have led to the death of a subject, or user or of other persons or to a serious deterioration in their state of health.

Indirect harms to the patients are not possible to occur as the test result will only be known after individual study end. Hence, any incorrect results of the test can have no consequence for the further course of the patient during the study.

All incidents are to be recorded on a separate paper form. A description of the event, including the start date, resolution date, action taken, and the outcome should be provided. As a general principle, there should be a pre-disposition to report rather than not to report in case of doubt on whether or not to report an incident. Any report should not be unduly delayed because of incomplete information.

4.4 Documentation of Medication

Concomitant medication will be documented at each visit. Any changes from previous visits found, however, will not be followed up as a possible indication of an adverse event.

5 Diagnostic Criteria and Definition of Analysis Groups

5.1 Pregnancy Endpoints

The study will have to use various pregnancy endpoints for various analyses. For the analysis of the primary objective and some of the secondary objectives the endpoint will be clinical pregnancy on day 21* (+4/-3) defined as detection of embryo sac by US, regardless of whether or not there will be a miscarriage during the later course of the 1st trimester. For some other secondary objectives the endpoint will be ongoing pregnancy on day 65 (+7) defined as detection of fetal heart beat by US at this time point or later). Detection of embryo sac/fetal heart beat on day 65 (+7) replaces missing detection of embryo sac on day 21 (+4/-3) for the definition of clinical pregnancy.

For pregnancy on day 11 (+2) as an individual endpoint and for the allocation of patients to categories as described below (negative and biochemical pregnancy in particular) a cut-off value for hCG+β on day 11 (+2) of >10 mIU/mL will be used as per practice at the study site.

For the purposes of the analysis with respect to secondary objective no. 11 there will be 5 disjunct pregnancy categories:

1) Negative pregnancy

hCG+β on day 11 (+2) ≤10 mIU/mL, unless clinical pregnancy, ectopic pregnancy, ongoing pregnancy or 1st trimester miscarriage are detected at a later stage

2) Ectopic pregnancy

Rules out the remaining categories 3), 4) and 5)

3) 1st trimester miscarriage

Rules out (supersedes) categories 4) and 5)

4) Ongoing pregnancy on day 65 (+7)

5) Biochemical pregnancy

hCG+ β >10 mIU/mL on day 11 (+2) and no clinical/ongoing pregnancy at any stage and no ectopic pregnancy and no signs or symptoms of a 1st trimester miscarriage.

The following patients are ineligible for the analysis with respect to secondary objective no. 11: hCG+ β on day 11 (+2) >10 mIU/mL, missing data on ectopic pregnancy/ presence of embryo sac, fetal heart beat and no 1st trimester miscarriage.

1st trimester miscarriage will always be assumed in cases with detection of embryo sac on day 21 (+4/-3) and no ongoing pregnancy on day 65 (+7). It should be noted that per-protocol patients with this constellation will be included in the group of subjects with clinical pregnancy on day 21 (+4/-3) for the primary analysis of the study.

*All days mentioned in this section are counted from ET (=Day 0).

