- Taking of a further 6 mL of venous blood for asservation of 0.5 mL of serum (to be kept in the freezer at -80°C with temperature log and shipped in batches for the central analysis of hhCG), of a further 0.5 mL for IVI kept in the freezer at -80°C and of another of 2.0 mL kept in the freezer at -80°C for to be shipped to Roche at the end of the study.
- Concomitant diseases and medication.

Visit 3

At Visit 3 the following will be done and documented in the eCRF:

- Measurement and documentation of serum estradiol, progesterone and hCG+ß by the study site
- Separation of 6 mL of blood taken in addition to routine blood sampling for asservation of 0.5 mL of serum (to be kept in the freezer at -80°C with temperature log and shipped in batches for the central analysis of hhCG), of a further 0.5 mL for IVI kept in the freezer at -80°C and of another 2.0 mL kept in the freezer at -80°C for to be shipped to Roche at the end of the study.
- Concomitant diseases and medication.

Visit 4

At Visit 4 the following will be done and documented in the eCRF:

- Concomitant diseases and medication
- Ultrasound for detection of embryo sac, (heart beat) or ectopic pregnancy.

Visit 5

At Visit 4 the following will be done and documented in the eCRF:

- Concomitant diseases and medication
- Ultrasound for detection of embryo sac, heart beat or ectopic pregnancy.

Visit 6

At Visit 5 the following will be done and documented in the eCRF:

- Concomitant diseases and medication
- Documentation of pregnancy category: negative pregnancy, ectopic pregnancy, 1st trimester miscarriage, ongoing pregnancy (single/multiple) on day 65 (+7), biochemical pregnancy (see section 5.1)
- Incidents and indirect harms
- Final documentation.

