2.5 Endpoints of the Study

2.5.1 Primary Endpoint

AUC of the ROC curve for hhCG and hCG+β on day 4 (+1) after ET for the prediction of clinical pregnancy on day 21 (+4/-3) after ET (=6 weeks after last menstruation, detection of embryo sac by US).

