5.2 Patient Group for the Primary Analysis

The primary analysis of the study will be carried out in the per-protocol group. This will include patients who have met all inclusion criteria, violated no exclusion criterion and for whom the data for the evaluation of the primary objective have been determined in compliance with the stipulations of this protocol (i.e. valid results for hhCG and hCG+ β on day 4 (+1)* and for US on day 21* (+4/-3).Ongoing pregnancy on day 65 (+7) replaces missing US data for day 21 (+4/-3) as to the question of ongoing pregnancy on this day.

*Days mentioned in this section are counted from ET (=Day 0).

6 Patient Insurance

IVI Valencia undertakes to insure liability for potential damage caused to a subject in connection with the trial and provides insurance policy for all study subjects.

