7.3 Groups for Biostatistical Analysis

The population of **patients enrolled** will include all patients who gave informed consent.

The **patients treated** population will consist of all patients for whom the IVF-ET was performed.

The per-protocol population will consist of all eligible patients treated, i.e. will be restricted to those patients of the **patients treated** population who did not violate any eligibility criteria and who have available measurements for both hhCG and hCG+ β on day 4* (+1) and an assessment of clinical pregnancy on day 21* (+4/-3). A missing assessment of clinical pregnancy on day 21 (+4/-3) can be replaced by an assessment of ongoing pregnancy on day 28 (+4/-3) and/or 65 (+7).

In case of sufficiently high numbers of multiple pregnancies, subgroup analyses may be performed for patients with multiple and single pregnancies. Further subgroups of interest, if any, will be defined in the Statistical Analysis Plan.

*All days mentioned in this section are counted from ET (=Day 0).

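### A sac first seen on the day-28 scan, after a day-21 scan that showed none, does not count as clinical pregnancy in the primary analysis if the pregnancy is lost before day 65

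*Combined protocol and SAP*

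**What the plan says.** Sections 2.5.1 and 5.1 set the primary outcome as "clinical pregnancy on day 21* (+4/-3) defined as detection of embryo sac by US, regardless of whether or not there will be a miscarriage" in the rest of the first trimester. The Schedule of Assessments puts ultrasound at Visit 4, day 21 (+4/-3), and again at Visit 5, day 28 (+4/-3). Section 2.4 describes the Visit 4 scan as "Ultrasound for detection of embryo sac, (heart beat) or ectopic pregnancy", and the Visit 5 scan also looks for the sac.

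Three sections say what may stand in for the day-21 result:

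- **5.1 (endpoint definition):** "Detection of embryo sac/fetal heart beat on day 65 (+7) replaces missing detection of embryo sac on day 21 (+4/-3"). Day 28 is not named.
- **5.2 (primary analysis group):** "Ongoing pregnancy on day 65 (+7) replaces missing US data for day 21 (+4/-3"). Day 28 is not named here either.
- **7.3 (per-protocol population):** "A missing assessment of clinical pregnancy on day 21 (+4/-3) can be replaced by an assessment of ongoing pregnancy on day 28" and/or day 65.

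Section 5.1 also assigns 1st trimester miscarriage automatically when a sac was seen on day 21 and there is no ongoing pregnancy on day 65.

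**The concern.** The definition is meant to include pregnancies that are later lost. Yet a pregnancy whose sac is first seen at Visit 5 and which then miscarries has no route into the positive group once a Visit 4 scan has been done. She enters the negative group of the primary ROC comparison, and a high day-4 value of either marker is then scored as a false positive.

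The treatment is also uneven. Under 7.3, a woman who skips Visit 4 can be classified from day 28. The same woman, had she attended on day 18 with no sac visible, cannot. The same coding feeds secondary objectives 1, 4, 6 and 8 wherever they use clinical pregnancy on day 21. If such cases are settled after the hhCG results are known, that is a post-hoc decision about the primary endpoint.

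**Working it through.** **1. Windows.** Visit 4 runs from 21 − 3 = day 18 to 21 + 4 = day 25. Visit 5 runs from 28 − 3 = day 25 to 28 + 4 = day 32. They meet on day 25, so a sac seen exactly then could be claimed for either visit. What follows concerns sacs first seen after day 25.

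**2. Coding under each rule** (no sac at Visit 4 unless stated, sac at Visit 5):

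| Case | 5.1 | 5.2 | 7.3 | Primary coding |
|---|---|---|---|---|
| Lost before day 65 | no pregnancy on day 65 to replace with | not triggered, US data exist | not triggered, assessment exists | not pregnant |
| Ongoing on day 65 | applies only if *missing detection* covers a scan that saw no sac | not triggered | not triggered | depends on that reading |
| Visit 4 missed, lost before day 65 | day 65 only | day 65 only | day 28 may be used | depends on section |

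The first row has one answer whichever way the text is read.

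**3. The plan's own power.** Inputs from 7.1: AUCs 0.67 and 0.79, 61 positives, 75 negatives, correlation 0.6 between tests, one-sided alpha 0.025, stated power 0.8022. With z = Φ⁻¹(A):

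- Var(A) = [A(1−A) + (n₁+n₀−2)(Φ₂(z,z;0.5) − A²)] / (n₁n₀). This gives standard errors of 0.0462 and 0.0385.
- Cov = [f(0.6) + (n₁+n₀−2) f(0.3)] / (n₁n₀), with f(r) = Φ₂(z₁,z₂;r) − A₁A₂. The correlation between the AUCs is 0.555.
- SE under the null (both AUCs 0.67) = 0.0436; under the alternative = 0.0405.
- Power = Φ[(0.12 − 1.96 × 0.0436) / 0.0405] = 0.803.

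This reproduces the plan's figure. The plan does not state its exact variance convention. Using only the alternative variance gives 0.825 to 0.841.

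**4. If k pregnancies are coded negative and their markers are typical.** The number k is an assumption. The contaminated share of negatives is w = k/(75+k), each AUC becomes (1−w)·AUC + w·0.5, and the group sizes become 61−k and 75+k.

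| k | w | AUCs | Difference | Power |
|---|---|---|---|---|
| 0 | 0 | 0.670 / 0.790 | 0.120 | 0.803 |
| 1 | 1/76 = 0.013 | 0.668 / 0.786 | 0.118 | 0.789 |
| 3 | 3/78 = 0.038 | 0.663 / 0.779 | 0.115 | 0.760 |
| 6 | 6/81 = 0.074 | 0.657 / 0.768 | 0.111 | 0.716 |

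A Hanley-McNeil variance with an assumed AUC correlation of 0.54 starts at 0.813 and gives 0.797, 0.764 and 0.713.

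**5. If their markers are not typical.** I simulated 6,000 studies from the binormal inputs in 7.1 and moved 3 of the 61 positives to the negative group:

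| Which 3 are moved | AUC hCG+β | AUC hhCG | Difference |
|---|---|---|---|
| none | 0.670 | 0.791 | 0.121 |
| at random | 0.663 | 0.780 | 0.117 |
| lowest on both markers combined | 0.707 | 0.822 | 0.116 |
| lowest on hhCG | 0.693 | 0.828 | 0.135 |
| lowest on hCG+β | 0.711 | 0.808 | 0.097 |

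The last three rows are extremes, not forecasts. They show that both AUCs can rise and that the difference can move either way.

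**The case against.** An endpoint fixed in time is a legitimate prespecified choice, and the 45% pregnancy rate in 7.1 is itself stated for day 21. The group at issue is narrow and may be empty. Several stronger readings are tempting, and the documents do not support them:

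- *Every late-visible pregnancy is coded not pregnant.* Section 5.1 speaks of missing detection, where 5.2 speaks of missing data and 7.3 of a missing assessment. It can fairly be read as letting pregnancy on day 65 override a scan that saw no sac. Negative coding is certain only for losses before day 65.
- *The outcome always rests on one scan.* A missing day-21 result can be replaced from day 65 and, under 7.3, from day 28.
- *Later scans are never used.* In the five categories for secondary objective 11, negative and biochemical pregnancy both exclude pregnancies found later, and Visit 6 records the category directly. The automatic miscarriage rule needs a day-21 sac, but nothing shows it is the only route into that category.
- *Power is certain to fall, or the missed women are mainly failing pregnancies.* The documents give neither the frequency of unseen sacs on days 18 to 25 nor the marker levels of such women.

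All of this limits the reach of the point. What remains is that no rule lets a sac on day 28 change a completed negative day-21 scan in the primary analysis. That sits badly with the plan's stated indifference to later miscarriage and with its own use of day 28 in 7.3.

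**Conclusion.** The point holds in a narrow form. For a woman with no sac on day 21, a sac on day 28 and a loss before day 65, the coding is not pregnant on any reading. For one still pregnant on day 65, it is undefined until *missing detection* is defined. The effect size is unknown. The fall in power to 0.79, 0.76 or 0.72 for 1, 3 or 6 affected pregnancies is one scenario, which assumes typical marker values and no recoding on day 65. With low day-4 values among the missed women, the AUCs would tend to be inflated instead. The sample size calculation is not in error. The sponsor should make the change because the second scan is already scheduled and the rule can be settled before any hhCG result is seen.

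**What to change.** Replace the separate statements in 2.5.1, 5.1, 5.2 and 7.3 with one rule. Clinical pregnancy is an embryo sac on ultrasound at Visit 4 or Visit 5, or pregnancy confirmed on day 65; a woman is negative only if none of these is seen. Define *missing detection*, saying whether it covers a scan that was done and saw no sac. State how a negative Visit 4 scan is coded when Visit 5 was not attended, so that such women are not lost from the per-protocol group by accident. Apply the same rule to the automatic 1st trimester miscarriage assignment in 5.1.

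If the sponsor prefers to keep day 21 alone as primary, prespecify the version above as a sensitivity analysis and report how many women change group.

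The cost is wording, with no added visit or scan. For the scan-based part, outcome status closes on day 32 instead of day 25, about a week later. Waiting for day 65 is already built into the present replacement rules.

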1.2 Background and Study Rationale

1.2.1 Background

Hyperglycosylated human chorionic gonadotropin (hhCG) as it was later called was first isolated from the urine of women with invasive trophoblastic disease [2]. It is a hyperglycosylated isoform of human chorionic gonadotropin (hCG) with more extensive and more complex carbohydrate moieties than hCG during the initial 3 weeks of pregnancy hhCG is the primary hCG isoform [3–9]. It is synthesized primarily by cytотrophoblasts, whereas hCG is produced by syncytiotrophoblasts [12, 13]. hhCG is supposed to be of relevance during implantation into the uterine wall [13–15]. The monoclonal antibody against hhCG, B152, has a specificity for hhCG of >99 % relative to hCG [4, 8, 10], whereas many other antibodies against hCG show significant cross reactivity with hhCG [11].

Urinary hhCG levels during pregnancy were shown to rise 3 days sooner on average than those of hCG. The ratio of hhCG to hCG may allow to differentiate between clinical and biochemical pregnancy [5].

In a retrospective monocenter evaluation in 112 women with in vitro fertilization (IVF), fresh embryo transfer (ET) and day-9 and day-16 after egg retrieval (equals days 4 and 11 after ET) serum samples carried out by Chuan et al. it was found that a day-9 hhCG level of >110 pg/mL was 96% specific for ongoing pregnancy, yielding a positive predictive value of 94%. Compared with the day-9 hCG level, hhCG was more sensitive and had a larger area under the curve (0.87 vs. 0.67, respectively). In contrast, the diagnostic test characteristics were similar between the day-16 hhCG and hCG levels [16]. In a prospective blinded clinical trial by Strom et al. enrolling 58 IVF-ET patients a single serum or urine hhCG measurement identified pregnancies (both biochemical and clinical) on day 6 post ET with 100% sensitivity and specificity, whereby it was possible to identify biochemical pregnancies by their lower hhCG values [17].

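### Section 5.1 divides losses without a sac between biochemical pregnancy and miscarriage by symptoms that the protocol neither defines nor schedules

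*Combined protocol and SAP*

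**What the plan says.** Section 5.1 announces that "there will be 5 disjunct pregnancy categories" for secondary objective 11. The parts that matter here are these.

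- **Clinical pregnancy** is "defined as detection of embryo sac by US, regardless of whether or not there will be a miscarriage during the later course of the 1st" […], so a later loss does not undo it.
- **Category 1 (negative)** requires hCG+β of at most 10 mIU/mL on day 11 (+2), "unless clinical pregnancy, ectopic pregnancy, ongoing pregnancy or 1st trimester miscarriage are detected at a later stage".
- **Category 3 (miscarriage)** has no definition under its own heading, only a place in the hierarchy: "Rules out (supersedes) categories 4) and 5". A later sentence gives the one allocation rule: "1st trimester miscarriage will always be assumed in cases with detection of embryo sac on day 21 (+4/-3) and no ongoing pregnancy on day 65".
- **Category 5 (biochemical)** requires a day-11 hCG+β above the 10 mIU/mL cut-off, together with "no clinical/ongoing pregnancy at any stage and no ectopic pregnancy and no signs or symptoms of a 1st trimester miscarriage".
- **Ineligible for objective 11** are women with hCG+β above 10 mIU/mL, "missing data on ectopic pregnancy/ presence of embryo sac, fetal heart beat and no 1st trimester miscarriage".

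Section 7.6.2 uses the categories to describe the course of hhCG and hCG+β with summary statistics. The Schedule of Assessments and Section 2.4 list no item for signs or symptoms of miscarriage.

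**The concern.** Whether a sac was seen separates a biochemical loss from the loss of a clinical pregnancy, and the protocol's own definition of clinical pregnancy rests on it. The symptom clause brings a second criterion into category 5. Two women with the same day-11 hCG+β and the same empty ultrasound can then be filed differently because one of them had a symptom noted.

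Objective 11 asks how well absolute values and changes in hhCG distinguish the five outcomes. Section 1.2.1 cites a prospective study in which "it was possible to identify biochemical pregnancies by their lower hhCG values". If losses without a sac do have lower hhCG, placing some of them in the miscarriage category blurs the contrast that objective 11 is meant to show. If they fall into no category, category 5 becomes a selected remainder of the biochemical losses.

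**Working it through.** The plan gives no figure to reproduce, so the check is one of definitions.

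**Step 1: apply the rules.** Take women with hCG+β above 10 mIU/mL on day 11, complete ultrasound data, no ectopic pregnancy and no ongoing pregnancy on day 65. Categories 1, 2 and 4 are closed to all of them. Cross sac on day 21 with symptoms:

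| Sac seen | Symptoms recorded | Category 5 open? | Result under Section 5.1 |
|---|---|---|---|
| No | No | Yes | 5, biochemical |
| No | Yes | No (symptom clause) | 3 by elimination, or none |
| Yes | No | No (clinical pregnancy) | 3 (always-assumed rule) |
| Yes | Yes | No (clinical pregnancy) | 3 (always-assumed rule) |

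The second row is the problem. With ultrasound data complete, the ineligibility sentence does not remove these women.

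**Step 2: does category 3 require a sac?** The always-assumed sentence gives a sufficient condition, not a necessary one. Three features of Section 5.1 suggest that a sac is not needed:

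- The category 1 exception lists miscarriage and clinical pregnancy as separate events.
- The ineligibility sentence removes women with missing sac data only when there is no miscarriage, so miscarriage can be assigned without sac data.
- Category 5 already excludes any clinical pregnancy. If miscarriage presupposed a sac, the symptom clause would exclude nobody further.

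The reading in which row 2 goes to category 3 is therefore the better supported. If the sac rule is nevertheless taken as the full definition, row 2 fits no category. On either reading these women leave category 5.

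**Step 3: are symptoms collected?** Section 2.4 rules out general AE collection. Sections 2.5.3 and 4.3.1 limit AE recording to the two study blood draws. Concomitant diseases are documented at visits, but nothing requires miscarriage symptoms to be entered there, and no visit falls between day 11 and day 21.

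**Step 4: how many women?** Let b be the biochemical losses, s the losses after a sac, and p the share of b with symptoms recorded. If row 2 goes to category 3:

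- share of category 3 without a sac = pb / (pb + s)
- women left in category 5 = b(1 − p)

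The documents give none of b, s or p. As assumptions only, take b as 8–15% of 136 (11 to 20) and s as 10–20% of 61 (6 to 12):

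| p | Lowest share (b = 11, s = 12) | Highest share (b = 20, s = 6) | Left in category 5 |
|---|---|---|---|
| 0 | 0% | 0% | 11 to 20 |
| 0.1 | 1.1/13.1 = 8% | 2/8 = 25% | 9.9 to 18 |
| 0.5 | 5.5/17.5 = 31% | 10/16 = 63% | 5.5 to 10 |
| 1 | 11/23 = 48% | 20/26 = 77% | 0 |

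The result is governed by p, about which the documents say nothing.

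**The case against.** The strongest reply is that Section 5.1 never mentions bleeding, never says what counts as a sign or symptom, and never states that a woman without a sac goes to category 3. That step needs the five categories to be exhaustive, whereas the text says only that they do not overlap. Section 2.4 has the pregnancy category documented at Visit 6 without saying whether a derivation or the investigator's diagnosis decides, so an investigator could record such a woman as biochemical. With so little symptom collection, the clause may hardly operate.

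Much of this stands, and it limits the claim. A reader might infer that biochemical pregnancies ending in bleeding are systematically filed as miscarriages, that category 5 is nearly emptied, or that a third to three quarters of category 3 never had a sac. The documents do not support any of these. They depend on outside rates and on symptoms being recorded in at least half of biochemical losses, which the limited collection gives no reason to expect. Even at half, category 5 keeps half its women.

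A reader might also infer damage to the main results. There is none: the primary endpoint depends on the sac (or its day-65 replacement), and the AUC, sensitivity and specificity analyses for clinical, ongoing and day-11 pregnancy do not use these categories.

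The reply does not remove the defect itself. The clause is a stated exclusion, and it separates women with identical hCG+β and ultrasound results. If it seldom operates, that is because of incomplete recording and not because the definition is sound.

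**Conclusion.** The point holds as a defect of definition in a descriptive secondary analysis and should be corrected. A loss without a sac but with recorded symptoms is barred from biochemical pregnancy and goes to miscarriage by elimination, or to no category on the narrower reading. The deciding observation is undefined and unscheduled, so the allocation may not be reproducible.

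The effect is confined to the by-category summaries for objective 11 and endpoint 14. Its size runs from near 0 to most biochemical losses, depending on how often symptoms are recorded, and no narrower range can be drawn from the documents. Mixing within category 3 further assumes that the categories are exhaustive; loss from category 5 does not.

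**What to change.** In Section 5.1:

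1. Define category 3 as loss after an intrauterine sac or heart beat was seen on any study ultrasound (Visit 4, Visit 5 or the day-65 assessment). This also covers a sac first seen after day 21, which the always-assumed rule omits.
2. Define category 5 as hCG+β above 10 mIU/mL on day 11 (+2), ultrasound performed with no sac on any scan, no ectopic pregnancy and no ongoing pregnancy.
3. Delete the symptom clause from category 5.
4. Align the category 1 exception and the ineligibility sentence with these definitions. Women with hCG+β above 10 mIU/mL and missing ultrasound must not become biochemical by default. Those with a reported miscarriage but no ultrasound should be listed separately or excluded from objective 11.

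The cost is a few sentences and one revised derivation, with no added visit or sample: hCG+β is measured at Visit 3 and ultrasound is scheduled at Visits 4 and 5. The Schedule of Assessments shows no ultrasound at Visit 6, although Section 2.1 describes one at the final visit and Section 5.1 relies on day-65 findings, so the text should name the source of the day-65 data. The downside is that a few women with a reported miscarriage but no ultrasound may leave the objective 11 summaries.
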